3.2.1 PRIMARY ENDPOINT

The difference between the temperature as measured on each cheek at the level of the top of the alar rim and in between the lateral limbus. (The following is an example of a test subject before the trial to ensure the technology could measure what was needed in the trial – these are not results but an example of what the results would look like).

Sample Thermal Analysis

3.2.2 SECONDARY ENDPOINTS

- The difference in the number of adverse events between the two sides of the face
- The difference in pain scores on each side of their face as rated by subjects
- The difference in patient satisfaction scores when rating the procedure on the left and right side of their face
- The difference in erythema on the left and right side of subject's faces as graded by blinded evaluators doing live assessments 30 minutes after the procedure
- The difference in healing time in daily photographs as rated by blinded evaluators

These endpoints will show if the Velez Intense Hydration face mask decreases skin temperature after a cosmetic procedure, if subjects are happy with the use of the mask, and if they provide significant reduction in pain, erythema, and healing time.

4 STUDY ENROLLMENT AND WITHDRAWAL

4.1 PARTICIPANT INCLUSION CRITERIA

To be eligible to participate in this study, an individual must meet all the following criteria:

- Provision of signed and dated informed consent form
- Stated willingness to comply with all study procedures and availability for the duration of the study
- Male or female, aged 21 or over
- In good general health as evidenced by medical history
- For females of reproductive potential: use of highly effective contraception and a negative urine pregnancy test before laser treatment

4.2 PARTICIPANT EXCLUSION CRITERIA

An individual who meets any of the following criteria will be excluded from participation in this study:

- Subjects with active auto-immune conditions
- Subjects with a history of severe anaphylactic reactions
- Subjects with cancer, or other life-threatening medical condition
- Subjects taking prescribed anti---coagulants, chemotherapy, immunosuppressive agents, or immunomodulatory agents, in the 2 weeks prior to the study.
- Subjects with tattoos or many skin growths on the face that would obscure visualization of patient erythema
- Subjects with a history of keloid or hypertrophic scar on the face
- Subjects unwilling or unable to sit still while having the laser procedure, the mask application, or the photographs
- Subjects who are pregnant or nursing
- Subjects with any facial bruising, swelling, or erythema at baseline
- Subjects with current skin infections, tumors, herpes outbreak or dermatitis on the face
- Any medical condition that in the opinion of the Investigator would make the subject unsuitable for inclusion

4.3 STRATEGIES FOR RECRUITMENT AND RETENTION

- Participants will be compensated for their participation in the study by having the opportunity to improve their aesthetic appearance without any cost to the subject.
- Subjects will receive both text, email, and phone call reminders for their scheduled visit.
- 5 subjects will be needed in each arm of the study to accommodate for a 10% expected dropout rate to have at least 4 subjects complete the study in each arm.
- The source of the subjects will be those who visited Siperstein Dermatology Group and allowed their information to be used to be contacted for promotions and trials. This list includes over 5,000 patients.

- The subjects on this list will first be contacted via email to see if they are interested in the trial. If they respond, they will then be sent a subject questionnaire to screen for those who satisfy the inclusion/exclusion criteria. The first 15 subjects that satisfy these criteria will be scheduled for the trial.

4.4 PARTICIPANT WITHDRAWAL OR TERMINATION

4.4.1 REASONS FOR WITHDRAWAL OR TERMINATION

Participants are free to withdraw from participation in the study at any time upon request. An investigator may terminate participation in the study if:

- The participant's health declines requiring hospitalization
- The participant needs any surgery or other serious medical interventions
- The participant meets an exclusion criterion (either newly developed or not previously recognized) that precludes further study participation.
- The participant fails to show up for the visit.

4.4.2 HANDLING OF PARTICIPANT WITHDRAWALS OR TERMINATION

The primary investigator will call, email, write or visit all participants that have withdrawn or terminated from the trial if they are unable to make their visits to ensure all safety parameters have been met.

4.5 PREMATURE TERMINATION OR SUSPENSION OF STUDY

This study may be suspended or prematurely terminated if there is sufficient reasonable cause. If the study is prematurely terminated or suspended, the PI will promptly inform the IRB and Velez as well as provide the reason(s) for the termination or suspension.

Circumstances that may warrant termination or suspension include, but are not limited to:

- Determination of unexpected, significant, or unacceptable risk to participants
- Insufficient compliance to protocol requirements

Study may resume once concerns about safety, protocol compliance, or data quality is addressed and satisfy the IRB.

5 STUDY AGENT

5.1 STUDY AGENT(S), ACQUISITION & STORAGE

5.1.1 ACQUISITION

Velez Intense hydration masks will be supplied by Velez.

5.1.2 FORMULATION

Velez intense hydration masks are made of bio cellulose material obtained from vegetable raw materials and are self-adhering providing mobility and immediate comfort.

5.1.3 PRODUCT STORAGE AND STABILITY

The product will be stored in its original package in an air-conditioned building with temperatures ranging from 72-78 degrees Fahrenheit. The product will remain in a locked cabinet until it is ready to be used on subjects.

5.1.4 PREPARATION

The subject's face will be cleansed with a cleansing cloth to remove all topicals such as make-up, sunscreen, and moisturizers. A topical numbing cream will be applied for 30 minutes and then removed before the subject's face will be cleansed with alcohol immediately prior to the laser procedure.

The product will be removed from original packaging, cut in half with a sterile scissor, and placed on the subject's assigned side within 5 minutes of the end of the procedure.

5.1.5 DOSING AND ADMINISTRATION

Each subject will receive half of the Velez Intense Hydration Mask on either their left or right side according to randomization.

5.1.6 ROUTE OF ADMINISTRATION

The mask will be placed topically on the skin

5.1.7 DURATION OF THERAPY

The subject will remain in the office for 30 minutes with the Velez face mask applied immediately after their laser treatment.

5.1.10 TRACKING OF DOSE

The study coordinator will check each package of the facemask to ensure it was used properly

5.2 STUDY AGENT ACCOUNTABILITY PROCEDURES

The product will be shipped from Velez. Once received the Study Coordinator will place the product in a locked cabinet until it is ready to be used on subjects. The Study Coordinator will oversee assigning the product to each subject and ensuring before the subject leaves that they had received the correct face mask on the correct side of the face.

6 STUDY PROCEDURES AND SCHEDULE

6.1 STUDY PROCEDURE/EVALUATIONS

6.1.1 STUDY SPECIFIC PROCEDURES

- Medical history obtained from baseline subject questionnaire and verbally verified
- Examination by blinded evaluators
- Canfield photo imaging
- Counseling the subjects on the laser treatment and mask that they will be receiving
- Counseling the subjects that they will be given a facial mask on one side of their face only
- The study coordinator will check before the subject leaves that all appropriate photos and paperwork have been completed.

6.1.2 STANDARD OF CARE STUDY PROCEDURES

The *subjects'* skin will be wiped with a cleansing cloth and then alcohol prior to the laser procedure.

6.2 STUDY SCHEDULE

6.2.1 SCREENING

Screening Visit (Day -60 to 0)

- Send out and review subject questionnaires to determine eligibility based on inclusion/exclusion criteria.
- Schedule study visits for participants who are eligible and available for the duration of the study.
- Provide participants with specific instructions needed to prepare for first study visit and all subsequent visits.

6.2.2 ENROLLMENT/BASELINE

Enrollment/Baseline Visit (Visit 1, Day 0)

- Review in depth the study design with subjects and obtain informed consent of potential participants verified by signature
- Perform examination and verbally review subject's medications and medical history to determine eligibility based on inclusion/exclusion criteria.
- Verify all inclusion/exclusion criteria.
- Obtain demographic information
- Randomization
- Perform either a Sciton Moxi, Sciton Erbium, or Secret RF treatments to subject's face, and then apply a half mask on one side of the face according to randomized groups.
- Record adverse events as reported by participant or observed by investigator or blind evaluator.
- Perform protocol adherence check by study coordinator
- Collect post-procedure subject questionnaires
- Take post-procedure photos

- After photographs and blind evaluation both side of the face will be treated with the normal post-procedure care such as Vaseline for laser resurfacing and a Hydrating serum for Moxi and Microneedling. Additional masks will be given to patients to wear for 2 hours at home each day until deemed healed by the primary investigator.

6.3.3 FOLLOW -UP

Follow Up Visits (Visit 2-8, Day 1-7)

- Record adverse events as reported by participant on side assigned the mask
- Photograph with both thermal camera and Canfield standardized photography
- Primary investigator to advise each day if they need to return the next day or are done with the study and completely healed

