Objectives: Primary Objective: To assess the efficacy of a facial mask in decreasing facial skin temperature after three different aesthetic treatments

Important Secondary Objectives:

1. To determine the safety and incidence of adverse events when using a Velez face mask after 3 different aesthetic treatments
2. To assess the change in the level of pain when using a Velez face mask after aesthetic treatments
3. To assess patient satisfaction with use of a Velez face mask after aesthetic treatments
4. To assess erythema when using a Velez face mask after aesthetic treatments
5. To assess healing time when using a Velez face mask

Primary

Endpoints:

Primary Endpoint:

The difference between the temperature on the mid-cheek (point inferior to the lateral limbus).

Important Secondary Endpoints:

1. The difference in the number of adverse events between the two sides of the face
2. The difference in pain scores on each side of their face as rated by subjects
3. The difference in patient satisfaction scores when rating the procedure on the left and right side of their face
4. The difference in erythema on the left and right side of subject's faces as graded by blinded evaluators doing live assessments 30 minutes after the procedure
5. The difference in healing time on the left and right side of subject's faces as graded by blinded evaluators looking at daily photographs

Population: Healthy adults aged 21 and over living in Palm Beach County, Florida.

Sample Size: 15

Study Sites: [name] &
[name]

Duration: 7 days

Study Agent: Velez Intense Hydration Mask

SCHEMATIC OF STUDY DESIGN

- Total n=15
- Screen potential subjects by inclusion and exclusion criteria

Day 0 Randomization

- Obtain informed consent, randomize into one of the following two groups
- Treatment Group 1 Right Side Velez Intense Hydration Mask
- Treatment Group 2 Left Side Velez Intense Hydration Mask

Day 0 Baseline assessments/ Study Intervention

- Baseline Assessments:
 - Pre-procedure pictures taken with Canfield's imaging system (Front, Right and Left Views)
- Study Intervention:
 - 1st Arm (n=5)

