Non-ablative fractionated Thulium laser (Sciton Moxi) will be performed on level 3 and an Intense Hydration Mask will be applied to one side of the face with nothing on the other side for 30 minutes. After photos and evaluation, a hydration serum will be applied to both sides and patients will be sent home with masks to be worn at least 2 hours every day until deemed fully healed by the investigator
 - 2nd Arm (n=5)
Ablative full Erbium:Yag laser (Sciton Contour) will be performed at 200 microns and an Intense Hydration Mask will be applied to one side of the face with nothing on the other side for 30 minutes. After photos and evaluation, Vaseline will be applied on both sides of the face and the patient will be sent home with masks to be worn at least 2 hours every day until deemed fully healed by the investigator
 - 3rd Arm (n=5)
Microneedling with RF (Cutera Secret) will be done with a non-insulated needle at a depth of 200 and an Intense Hydration Mask will be applied to one side of the face with nothing on the other side for 30 minutes. After photos and evaluation, a hydrating serum will be applied on both sides of the face and the patient will be sent home with masks to be worn at least 2 hours every day until deemed fully healed by the investigator

All Arms

- Post-procedure pictures and questionnaires to be completed by subjects 30 minutes after the procedure
- Safety analysis and erythema scale to be performed by blind evaluators and a compliance analysis performed by study coordinator

Day 1-7 Follow-up assessments

- Daily in office follow-up assessments of study endpoints and safety until primary investigator deems patients healed from the procedure

1st Arm (n=5) Non-ablative fractionated Thulium laser (Sciton Moxi)

Post-procedure pictures and questionnaires to be completed by subjects for 3-7 days as determined daily by the primary investigator

2nd Arm (n=5) Ablative full Erbium:Yag laser (Sciton Contour)

Post-procedure pictures and questionnaires to be completed by subjects daily for 3-7 days as determined daily by the primary investigator

3rd Arm (n=5) Microneedling with RF (Cutera Secret)

Post-procedure pictures and questionnaires to be completed by subjects daily for 3-7 days as determined daily by the primary investigator

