6.3.7 SCHEDULE OF EVENTS TABLE

Procedures	Screening	Enrollment/Baseline Visit 1, Day 0	Day 1	, Day 2-	, Day 3-	, Day 4-	, Day 5-	, Day 6-	, Day 7-
Informed consent & Randomization		X							
Demographics & Medical History		X							
Aesthetic Treatment		X							
Subject Questionnaire	X	X	X	X	X	+/-X	+/-X	+/-X	+/-X
Exam for Adverse Effects		X	x	x	x	+/- x	+/- x	+/- x	+/- x
Exam by blinded Evaluator		X							
Intervention with Face Mask		X	x	x	x	+/- x	+/- x	+/- x	+/- x
Photos		X	x	x	x	+/-x	+/-x	+/-x	+/-x

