7 ASSESSMENT OF SAFETY

Safety evaluations for this study include an interview of the subjects to obtain information about any medical occurrence that meets the definition of an AE. Each subject should be questioned about AEs at the study visit following the screening visit. The question should be asked: "Since your last clinical visit have you had any health problems?" Information on AEs can also be obtained from signs and symptoms detected during the examination by the evaluator, which should include visual inspection of the treatment area.

AEs must be documented in the source document without regard for cause or relation to investigational product. If in the process of the interview, additional information regarding medical history or preplanned medical or surgical procedures is revealed, it must be documented in the source documents.

It is the responsibility of the Investigator to determine severity of the AE and relatedness of the event to the study product.

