7.5 RECORDING INSTRUCTIONS

Investigators, or other study site personnel, shall record all AEs including:

- a) Event term (recorded in standard medical terminology and avoiding abbreviations)
- b) Affected area
- c) Start date (first day with symptoms)
- d) Stop date (last day with symptoms)
- e) Intensity (mild, moderate, or severe)
- f) Seriousness (serious or not serious)
- g) Causal relationship to study product or study product injection procedure (yes or no)
- h) Action taken (none, medication treatment, non-pharmacological treatment, or other procedures/tests, subject withdrawn)
- i) Outcome of the AE (ongoing, recovered, recovered with sequelae, death, chronic/ stable, not recovered at the end of the study)

All AEs, non-serious as well as serious, are to be reported as an AE. The PI will record all reportable events with start dates occurring any time after informed consent is obtained until 7 (for non---serious AEs) or 14 days (for SAEs) after the last study intervention. At each study visit, the investigator will inquire about the occurrence of AE/SAEs since the last visit. Events will be followed for outcome information until resolution or stabilization.

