8.3 SAFETY ANALYSIS

Safety analysis will be descriptive only.

The number and percentage of subjects reporting each post-treatment symptom will be presented in total and by maximum severity.

A summary of all AEs will be provided, which will include:

- number of subjects with at least one AE and number of events (in total as well as serious AEs)
- number of subjects with at least one related AE and number of events (in total as well as serious AEs)
- number of subjects with at least one mild, moderate, and severe AE and number of events (in total as well as serious AEs)
- number of subjects with at least one unrelated AE and number of events (in total as well as serious AEs)
- number of subjects who did not have an AE

The number of subjects with AEs related to the study product as well as the number of events will be summarized, and action taken for related AEs will also be summarized. Serious AEs will be listed.

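### Section 6.3.3 ties Day 1–7 adverse event recording to the masked side, against the all-event rules and the between-side endpoint, and section 8.3 has no by-side summary

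*Combined protocol and SAP*

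**What the plan says.** The Protocol Summary and section 3.2.2 list as the first secondary endpoint: "The difference in the number of adverse events between the two sides of the face".

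The instructions for collecting AEs differ by section:

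- **Day 0 (6.2.2):** "Record adverse events as reported by participant or observed by investigator or blind evaluator". There is no side limit, and three sources are accepted.
- **Day 1–7, visits 2–8 (6.3.3):** "Record adverse events as reported by participant on side assigned the mask". Only one side and one source are named.
- **Schematic of Study Design, Day 1–7:** "Daily in office follow-up assessments of study endpoints and safety until primary investigator deems patients healed from the procedure". No side limit.
- **Schedule of events (6.3.7):** a row headed "Exam for Adverse Effects" is marked for Days 1–3 and, conditionally, Days 4–7. No side limit.
- **Section 7:** "AEs must be documented in the source document without regard for cause or relation to investigational product".
- **Section 7.5:** every AE is to be recorded, with the area affected as one field, and "At each study visit, the investigator will inquire about the occurrence of AE/SAEs since the last visit". Section 7.6.1 repeats the inquiry.

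For analysis, section 8.3 is descriptive. Its list begins with "number of subjects with at least one AE and number of events (in total as well as serious AEs") and continues by relatedness, severity and action taken. No item splits events by side or by mask versus no mask.

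**The concern.** A split-face comparison of AEs is fair only if both sides are observed and recorded in the same way. Both sides receive the laser or microneedling procedure. The procedure risks listed in section 2.3.1, such as swelling, itching, dermatitis and erythema, can appear on either side during the following week, and unmasked-side events are the comparator for the endpoint.

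The follow-up instruction asks staff to record events on the masked side and is silent on the other. Staff who work from the visit list would produce a count in which the unmasked side contributes almost nothing after Day 0. A mask with no effect on AEs would then look harmful, and a real reduction could be hidden or reversed.

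The analysis section adds a second gap. Each subject contributes both a masked and an unmasked side, so per-subject and overall totals cannot give a between-side difference.

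**Working it through.** The plan states no AE rate, AE sample size or AE power, so there is no figure of its own to reproduce. The check has three steps.

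**1. Do the texts conflict?** Section 6.3.3 is narrower than 6.2.2 on side and on source. It is narrower than 7, 7.5 and 7.6.1, which cover all AEs at every visit, and than the daily exam in 6.3.7. No section states an order of precedence. The conflict is in the wording itself.

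**2. Which way, and how far, could the count be distorted?** The inputs below are assumptions, because the documents supply none.

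- R = true mask to no-mask ratio of AEs
- f = share of AEs that occur on Day 0, the same on both sides
- c = share of unmasked-side Day 1–7 AEs that are recorded
- masked-side events are fully recorded

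With the true unmasked-side total set to 1, the recorded masked-side total is R and the recorded unmasked-side total is f + (1 − f)c. So:

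recorded ratio = R / [f + (1 − f)c]

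For equal true rates (R = 1):

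| Capture of unmasked-side Day 1–7 events | f = 25% | f = 50% | f = 75% |
|---|---|---|---|
| c = 0 (6.3.3 as written) | 1/0.25 = 4.0 | 1/0.50 = 2.0 | 1/0.75 = 1.33 |
| c = 0.5 | 1/0.625 = 1.60 | 1/0.75 = 1.33 | 1/0.875 = 1.14 |
| c = 1 (7 and 7.5 followed) | 1.0 | 1.0 | 1.0 |

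Now suppose the mask truly helps, with c = 0 and f = 50% of unmasked-side events.

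- If the mask halves AEs on Day 0 and afterwards alike, R = 0.5 and the recorded ratio is 0.5/0.5 = 1.0, that is, no difference.
- If it halves only the Day 1–7 AEs, the masked-side total is 0.5 + 0.25 = 0.75. The true ratio is 0.75 and the recorded ratio is 0.75/0.5 = 1.5.

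The same can be put as expected counts for the 15 subjects in section 8.1, with equal Day 0 rates on both sides and c = 0. The Day 0 terms cancel, so the recorded difference (mask minus no mask) is 15 × the masked-side Day 1–7 rate.

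| Assumed unmasked-side Day 1–7 events per subject | Mask has no effect: true → recorded | Mask halves Day 1–7 AEs: true → recorded |
|---|---|---|
| 0.1 | 0 → +1.5 | not computed |
| 0.3 | 0 → +4.5 | −2.25 → +2.25 |
| 0.5 | 0 → +7.5 | −3.75 → +3.75 |
| 1.0 | 0 → +15 | −7.5 → +7.5 |

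In these examples the sign reverses. The sizes depend on the assumed rates. The direction does not, because unmasked-side Day 1–7 events can only be lost.

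**3. Does any planned output report the endpoint?** Section 8.3 has no by-side line. The by-treatment presentation in 8.1 covers demographics, baseline assessments and subject characteristics, not AEs. The descriptive catch-all in 8.2 and 8.6 is limited to secondary effectiveness analyses. The endpoint therefore has no specified summary, even if every event is captured.

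**The case against.** The best defence is that 6.3.3 is a loosely worded bullet and does not say that only the masked side counts. The dedicated safety sections are mandatory in tone: 7 and 7.5 require every AE to be documented, 7.4.2 says to report when in doubt whether an observation is an AE, and 7.6.1 accepts events found in the questionnaires, which are scheduled at the follow-up visits. To lose unmasked-side events, staff would have to overlook several rules. On this view it is a drafting slip. The ratios come from chosen values of f and c, and the by-side count can be derived from the affected-area field. The endpoint is also descriptive, secondary and based on 15 subjects.

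Much of this stands. The bias is conditional, its size is assumed, and no test or error rate is involved. Nothing suggests that the sponsor intended one-sided recording.

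It does not remove the point. Section 6.3.3 is the instruction specific to the follow-up visits, and no text ranks it below section 7. The rule in 7.4.2 concerns whether an observation is an AE, not which section governs. The affected-area field helps only for events that were recorded, and 7.5 does not require it to say left or right. The gap in 8.3 remains even if every event is captured.

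**Conclusion.** The concern holds. Section 6.3.3 contradicts the Day 0 instruction, the all-event rules and the between-side AE endpoint. Followed as written, it can only bias the Day 1–7 comparison against the mask.

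The possible distortion runs from none (sections 7 and 7.5 followed) to a recorded ratio of 1.33 to 4.0 where the truth is 1.0 (6.3.3 followed, 25% to 75% of events on Day 0, equal true rates, full capture on the masked side). Those shares are assumptions. The conflict and the direction are not.

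Because Day 0 events have no side limit, the endpoint would be distorted, not impossible to estimate. The missing by-side summary in 8.3 is a smaller, separate defect. The consequences are confined to a descriptive secondary safety endpoint, and the primary temperature endpoint is untouched. This should be fixed before follow-up data are collected.

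**What to change.** 1. **Section 6.3.3:** replace the sentence with an instruction to record all adverse events on both sides of the face at every follow-up visit, whether reported by the participant or observed, stating the affected side (left, right, both, not facial). This brings it into line with 6.2.2, 7 and 7.5. Recording left or right, and linking to the allocation at analysis, means the recorder need not know which side had the mask.
2. **Section 7.5:** make that side a required entry in the existing affected-area field.
3. **Section 8.3:** add one descriptive table of subjects and events by masked and unmasked side, by severity, with the within-subject difference. State how events on both sides and non-facial events are counted. Keep the per-subject totals.

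The cost is one reworded sentence, one entry in an existing field and one table. If follow-up has already begun, establish which instruction the sites followed and report it with the comparison, because unrecorded unmasked-side events may be hard to reconstruct.

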7.4.2 RELATIONSHIP TO STUDY AGENT

All AEs will have their relationship to study agent or study participation assessed.

Evaluation of relatedness will consider etiologies such as natural history of the underlying disease, concurrent illness, concomitant therapy, study-related procedures, accidents, and other external factors.

The clinician’s assessment of an AE’s relationship to study agent is part of the documentation process, but it is not a factor in determining what is or is not reported in the study. If there is any doubt as to whether a clinical observation is an AE, the event should be reported. All AEs must have their relationship to study agent assessed. In a clinical trial, the study product must always be suspect. To help assess, the following guidelines are used.

- **Related** – The AE is known to occur with the study agent, there is a reasonable possibility that the study agent caused the AE, or there is a temporal relationship between the study agent and event. Reasonable possibility means that there is evidence to suggest a causal relationship between the study agent and the AE.
- **Not Related** – There is not a reasonable possibility that the administration of the study agent caused the event, there is no temporal relationship between the study agent and event onset, or an alternate etiology has been established.

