7.6 REPORTING PROCEDURES

7.6.1 ADVERSE EVENT REPORTING

The occurrence of an AE or SAE may come to the attention of study personnel during study visits and interviews of a study participant presenting for medical care, or upon review of subject questionnaires. Any medical condition that is present at the time that the participant is screened will be considered as baseline and not reported as an AE. However, if the study participant's condition deteriorates at any time during the study, it will be recorded as an AE. UPS will be recorded in the data collection system throughout the study. Changes in the severity of an AE will be documented to allow an assessment of the duration of the event at each level of severity to be performed. AEs characterized as intermittent require documentation of onset and duration of each episode. At each study visit, the investigator will inquire about the occurrence of AE/SAEs since the last visit. Events will be followed for outcome information until resolution or stabilization.

The FDA and IRB will receive notification of any UP or SAE within 24 hours of discovery by the primary investigator. All SAEs will be followed until satisfactory resolution or until the site investigator deems the event to be chronic or the adherence to be stable. The study sponsor will be responsible for notifying FDA of any unexpected fatal or life---threatening suspected adverse reaction as soon as possible but in no case later than 7 calendar days after the sponsor's initial receipt of the information.

The study investigator shall complete an Unanticipated Adverse Device Effect Form and submit to the study sponsor and to the reviewing IRB as soon as possible, but in no event later than 7 working days after the investigator first learns of the effect. The study sponsor is responsible for investigating and reporting the results of such evaluation to FDA and to all reviewing IRBs and participating investigators within 10 working days after the sponsor first receives notice of the effect.

A sponsor who conducts an evaluation of an unanticipated adverse device effect under 812.46(b) shall report the results of such evaluation to FDA and to all reviewing IRB's and participating investigators within 10 working days after the sponsor first receives notice of the effect. Thereafter the sponsor shall submit such additional reports concerning the effect as FDA requests (21 CFR 812.150(b)(1)).

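### Section 6.3.3 has staff record participant-reported adverse events on the mask side at Day 1-7 visits, which conflicts with the between-side adverse event endpoint and with the unrestricted rules elsewhere

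*Combined protocol and SAP*

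**What the plan says.** The Protocol Summary and section 3.2.2 both list as the first secondary endpoint "The difference in the number of adverse events between the two sides of the face".

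The instructions for collecting AEs differ by visit and by section:

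- **Day 0 (6.2.2).** AEs are recorded whether the participant reports them or the investigator or blinded evaluator sees them. No side is named.
- **Days 1-7 (6.3.3).** "Record adverse events as reported by participant on side assigned the mask". The control side is not mentioned, and neither are observed events.
- **Schematic of study design.** Endpoints and safety are to be assessed in the office daily during follow-up, with no side limit.
- **Schedule of events (6.3.7).** "Exam for Adverse Effects" is marked for Day 0 and Days 1-3, and conditionally for Days 4-7. No side is named. Subject questionnaires follow the same daily pattern.
- **Section 7.** "AEs must be documented in the source document without regard for cause or relation to investigational product".
- **Sections 7.5 and 7.6.1.** All AEs are to be recorded, and "At each study visit, the investigator will inquire about the occurrence of AE/SAEs since the last visit". Section 7.6.1 also names the review of subject questionnaires as a way AEs may come to light.

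For location, 7.5(b) asks for "Affected area" without saying that the side of the face must be given. Section 8.3 makes the safety analysis descriptive and lists AE summaries by subjects, events, seriousness, severity and relatedness. None of these is split by side.

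**The concern.** In a split-face trial the untreated side is the comparator. Section 2.3.1 lists swelling, itching, pain, dermatitis and erythema as risks of both the mask and the aesthetic procedures. A mask-side count alone therefore cannot separate what the mask causes from what the procedure causes. The control side can do so, but only if its events are collected by the same rule.

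The period matters too. On Day 0 the mask is worn for 30 minutes. After that it is worn at home for at least two hours a day until healing. Most mask exposure, and so most of the opportunity for mask-related events, falls in the period that 6.3.3 governs. A coordinator working from the visit list would find one rule for Day 0 and a narrower one for every later visit, and nothing in the protocol says which section prevails.

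**Working it through.** The plan gives no figure to reproduce here, and no AE rate or capture rate. The check is a comparison of the texts, with simple arithmetic for extent and direction.

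**1. What the endpoint needs.** Let M and C be the true numbers of participant-reported AEs on the mask and control sides during Days 1-7. The target for that period is M − C, so both must be collected on equal terms.

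**2. What 6.3.3 supplies.** It directs staff to collect M. It is silent on C.

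**3. What the other text supplies.** The schematic, 6.3.7, section 7, 7.5 and 7.6.1 each apply to the follow-up period or to AEs in general, and none limits the side. Followed in full, they collect both M and C.

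**4. Consequence.** Suppose all mask-side events are recorded and a fraction p of control-side events is caught through the routes in step 3. Then:

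- recorded difference = M − pC
- bias = (M − pC) − (M − C) = (1 − p)C

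The bias is never negative, so the mask can only look worse than it is. The two ends are:

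- p = 1 (the general rules catch everything): bias = 0.
- p = 0 (6.3.3 is read as exclusive and every other route fails): bias = C. With k events truly on each side, the recorded difference would be k instead of 0.

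Neither p nor C can be taken from the documents, so the bias can be given a direction but not a size.

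**5. Extent.** By 6.3.7, Days 1-3 are fixed and Days 4-7 conditional, giving 3 to 7 follow-up visits per subject. With all 15 subjects completing:

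- 15 × 3 = 45 subject-visits
- 15 × 7 = 105 subject-visits

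These are visits at which the instruction applies, not events lost.

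**6. Effect on inference.** Section 8.2 states hypotheses for temperature, pain, erythema and comfort, and none for AEs. Section 8.3 is descriptive. No test, p-value or sample size depends on this count.

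**The case against.** The strongest reply is that 6.3.3 does not exclude the control side. It names the mask side but does not say that only that side counts. The dedicated AE sections are mandatory and cover every AE, the investigator must ask at each visit, there is a daily adverse-effect exam, and the schematic calls for daily assessment of the endpoints, of which the between-side count is one. The daily questionnaires and photographs are further sources. The medical monitor's review of all AEs and the site monitoring in 7.8 are further checks. For control-side events to be lost, staff would have to read 6.3.3 as exclusive and also neglect these other duties.

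Most of this stands. A reader might infer from 6.3.3 that the protocol forbids recording control-side AEs, or that their count after Day 0 is zero by design. The documents do not support either reading, because several unrestricted requirements apply at the same visits.

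A reader might also infer from 7.5 and 8.3 that the endpoint cannot be reported at all. That does not follow either. The location item in 7.5(b) can hold the side, the endpoint definition in 3.2.2 already commits the trial to a between-side comparison, and the list in 8.3 need not be exhaustive. What is missing there is detail.

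The reply does not remove the conflict. The only AE instruction written for the follow-up visits themselves names one side, differs from the Day 0 instruction, and does not fit the endpoint it is meant to feed. The safety net also has limits. The blinded evaluator's exam is scheduled for Day 0 only, and the scripted AE question in section 7 is worded for the visit after screening.

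**Conclusion.** The point holds as an internal inconsistency that should be corrected. Section 6.3.3 conflicts with the between-side AE endpoint, with the Day 0 instruction in 6.2.2, and with the unrestricted rules in the schematic, 6.3.7, 7, 7.5 and 7.6.1.

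The conclusion is conditional. If staff follow 6.3.3 and the other routes do not catch every event, control-side AEs are undercounted and the comparison leans against the mask. This assumes that mask-side events are fully recorded. The bias is zero if the general rules are followed throughout, and its size cannot be derived from the documents. The primary temperature endpoint and all hypothesis tests are untouched. The point still matters because a named secondary endpoint should not depend on which section of the protocol a staff member happens to follow.

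**What to change.** **Main change.** Reword 6.3.3 so that AEs are recorded on both sides of the face at every follow-up visit, whether the participant reports them or staff observe them. This brings it into line with 6.2.2.

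**Supporting edits.**

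- In 7.5(b), have the location entry state the side: left, right, both or not facial.
- In 8.3, add a descriptive summary of AE counts by mask side versus control side, with events on both sides and non-facial events shown separately so that they are not forced into either count.

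**Cost.** One sentence in 6.3.3, one specified entry in 7.5(b) and one descriptive table in 8.3. There are no added visits, subjects or tests. Under 9.2 the amendment needs IRB approval before it takes effect.
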